STUDY PROTOCOL & STATISTICAL ANALYSIS PLAN

STUDY TITLE: ADAPTING AND IMPLEMENTING TEAMSTEPPS IN SCHOOL MENTAL HEALTH

NCT04440228

AUGUST 20, 2025

Project Aim 3 - Explore the feasibility, acceptability, and utility of TeamSTEPPS plus the strategies generated in Aim 2 on inter-professional collaboration, teamwork, and outcomes in schools.

PROTOCOL

Procedure. The primary implementation outcomes are feasibility and acceptability of the adapted TeamSTEPPS, consistent with recommendations for selecting appropriate outcomes for pilot phase research. We also explored collaboration and teamwork, assessed via self-report and observation, behavioral and educational outcomes for students, and potential contextual predictors of implementation which will allow us to identify measures that are sensitive to change for future trials. Inter-professional collaboration, which has been identified as a key factor in quality school mental health promotion, is assessed via self-report and observation. We will collect self-report data at baseline (i.e., before engagement in TeamSTEPPS) and for the school year following participation at two time points each school year (fall, spring).

Participants. Participants completing research measures include members of school mental health teams and school personnel from participating schools.

Dependent Variables and Measures

Self-Report Measures. Self-report measures of inter-professional collaboration and teamwork and feasibility and acceptability will be completed by participating mental health team members and school personnel.

Dependent measures:

Expanded School Mental Health Collaboration Instrument (ESMHCi). Mental health team members will complete the *Expanded School Mental Health Collaboration Instrument- Community version (ESMHCi-CV)*. School personnel will complete the *Expanded School Mental Health Collaboration Instrument- School version (ESMHCi-SV)*. The 59-item ESMHCi assess perceptions of three aspects of collaboration (i.e., types, influences, and benefits) between school professionals and mental health professionals from collaborating agencies on a continuous scale. Scores can be calculated individually or among groups working in the same school. For each subscale, an average score is calculated with higher scores indicating strengths and lower scores indicating areas to consider improving or targeting. Preliminary psychometric studies are promising and indicate validity and internal consistency.

TeamSTEPPS Teamwork Perceptions Questionnaires (T-TPQ). The T-TPQ is a self-report measure of individual perceptions of group-level team skills and behavior. It is based upon the five core components of teamwork that comprise TeamSTEPPS. Each construct is represented by seven questions, totaling 35 items. Items are rated continuously on a five-point scale from “strongly disagree” = 1 to “strongly agree” = 5. A total score is computed by averaging all items and higher scores indicate more favorable perceptions.

TeamSTEPPS Teamwork Attitudes Questionnaire (T-TAQ). The T-TAQ is a self-report measure of individual attitudes related to the core components of teamwork captured within TeamSTEPPS. Six items measure each of the core teamwork constructs, for a total of 30 items. Items are rated continuously on a five-point scale from “strongly disagree” = 1 to “strongly agree” = 5. A mean total score is calculated across items with higher scores indicating more positive attitudes.

The *Acceptability of Intervention Measure (AIM)* and *Feasibility of Intervention Measure (FIM)* are each reliable and valid 4-item tools to assess teacher, counselor, and leader perceptions of the acceptability and feasibility of TeamSTEPPS.

Exploratory contextual predictors

Evidence Based Practice Attitude Scale (EBPAS). The EBPAS is a 15-item self-report measure of attitudes toward adoption of EBPs. It consists of four subscales: appeal (is EBP intuitively appealing), requirements (would an EBP be used if required), openness (general openness to innovation), and divergence (perceived divergence between EBP and current practice). Items are rated from 0 (Not at all) to 4 (Very great extent). Higher scores indicate more positive attitudes, with the exception of divergence which is reverse coded.

Maslach Burnout Inventory Human Services Survey (MBI). The MBI is a 22 item self-report measure of burnout. Three subscales measure emotional exhaustion, depersonalization, and reduced personal accomplishment. Items are rated from 0 (Never) to 6 (Everyday) with higher scores on emotional exhaustion and depersonalization and lower scores on personal accomplishment (reverse scored) indicating higher levels of burnout.

Observations. We will conduct observations in schools who implement TeamSTEPPS. For each school observation, a trained observer from the research team will observe team dynamics, service provision, and interactions among mental health providers, school personnel, and students. Observations will occur at baseline (i.e., before engagement in TeamSTEPPS), at the completion of TeamSTEPPS trainings, and for 1 school year following participation at two time points each school year (fall, spring). Observations will include detailed field notes and use of the adapted *NOTECHS* for school mental health teams.

STATISTICAL DESIGN AND POWER

Qualitative analysis. We will load all field notes and interview transcripts into NVivo for data management and analysis. Analysis will be guided by an integrated analytic approach.

Quantitative analysis. Quantitative analysis of feasibility will examine the proportion of schools who enroll/those invited and participants who attend TeamSTEPPS training/those eligible to participate in the school. We also will examine the distribution of AIM and FIM scores to quantitatively assess acceptability and feasibility, respectively.

Collaboration and teamwork are assessed observationally (i.e., *NOTECHS*) and via self-report (e.g., *ESMHCI*, *T-TPQ*). Mean total and domain scores on the *NOTECHS* will be computed for each school. Individual and school scores will be calculated for the self-report measures.

The analytic approach consisted of three phases. First, preliminary analyses were conducted using paired t-tests to evaluate simple pre-to-post changes in the primary outcome measures: teamwork perceptions (T-TPQ), teamwork attitudes (T-TAQ), and collaboration (ESMHCI-SV). For the main analysis, we fitted linear mixed-effects regression models for each outcome variable, specifying random intercepts for participant ID to account for repeated measures and within-individual clustering. The core model included a binary post-training indicator as the primary predictor, along with the baseline value of the corresponding outcome as a covariate. To account for participant characteristics, we included a set of individual-level covariates: age, gender, race/ethnicity, education level, licensure status, professional role (clinical vs. school staff), years in the field, burnout (measured by the MBI-HSS subscales: emotional exhaustion, depersonalization, and personal accomplishment), and practice attitudes (EBPAS). These variables reflect clinician background, experience, and attitudes that may influence response to training. In parallel, we incorporated organizational-level covariates reflecting the structural and contextual features of training implementation. These included training group structure (small group, large group), school size, teacher-student ratio, building team size, and the number of team members trained. To examine whether training effects varied across these individual and organizational dimensions, we fitted comprehensive interaction models. These included all main effects plus full interaction terms between the post-training indicator and each individual- and organizational-level covariate. This allowed us to identify potential moderators of training impact and determine whether particular subgroups responded differentially to the intervention. Statistical significance was evaluated at the $\alpha = 0.05$ level.

Abbreviations

AIM	Acceptability of Intervention Measure
EBP	Evidence-based practice
EBPAS	Evidence-Based Practice Attitudes Scale
ESMHCI	Expanded School Mental Health Collaboration Instrument
FIM	Feasibility of Intervention Measure
MBI-HSS	Maslach Burnout Inventory – Human Services Scale
NOTECHS	Oxford Non-Technical Skills scale
TeamSTEPPS	Team Strategies and Tools to Enhance Performance and Patient Safety
T-TPQ	TeamSTEPPS Teamwork Perceptions Questionnaires

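### The mixed models carry a participant random intercept only, so tests of post-training by school-fixed moderators use too small a standard error if change differs between schools

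*Combined protocol and SAP*

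**What the plan says.** All places are in the combined protocol and SAP. Under Statistical Design and Power, Quantitative analysis, the linear mixed models for T-TPQ, T-TAQ and ESMHCI-SV are fitted "specifying random intercepts for participant ID to account for repeated measures and within-individual clustering". No other random effect, clustered standard error or school-level test appears there or elsewhere.

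Of the organizational covariates the same section says: "These included training group structure (small group, large group), school size, teacher-student ratio, building team size, and the number of team members trained". The interaction models add "full interaction terms between the post-training indicator and each individual- and organizational-level covariate", judged at the 0.05 level.

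The Participants section draws respondents from participating schools. School is identifiable in the data: "Individual and school scores will be calculated for the self-report measures". On ESMHCi the Dependent measures section says: "Scores can be calculated individually or among groups working in the same school". It describes the T-TPQ as a "self-report measure of individual perceptions of group-level team skills and behavior".

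The Procedure section makes feasibility and acceptability the primary implementation outcomes. It describes the other outcomes and the contextual predictors as explored, "which will allow us to identify measures that are sensitive to change for future trials".

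**The concern.** A moderator with one value per school is informed by as many independent units as there are schools, but a model with only a participant intercept counts participants. That intercept absorbs anything stable about a person, including the level of the person's school. It does not absorb a school's own amount of change.

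Shared change is plausible for T-TPQ, where colleagues rate the same team, and for ESMHCI-SV, which can be scored by school group. It is less so for T-TAQ, which records personal attitudes. The documents do not quantify it for any of the three.

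At stake is whether chance differences between schools are reported as moderators of training impact. If the overall change is also used to judge how measures would behave in other schools, its interval is too narrow for that purpose.

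**Working it through.** **Inputs.** From the documents: the random-effects structure, the covariate list, the 0.05 level (two-sided assumed), and self-report at baseline, fall and spring. The documents state no school count, respondents per school (m), ICC of change (ρ) or power figure, so there is nothing to reproduce. Assumed ranges: m = 4 to 6 (possible for ESMHCI-SV, completed by school personnel only) and 8 to 12; ρ = 0 to 0.15. Here ρ is the share of change-score variance lying between schools after the organizational interactions in the model.

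**Which moderators are school-fixed.** School size and teacher-student ratio certainly are. Building team size and the number trained probably are, which is an inference. Training group structure counts only if it is constant within school, which is not stated.

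**One post occasion.** With complete two-occasion data and no baseline covariate, the participant-intercept model is a regression of individual change on the moderator. Write τ² for the between-school and σ² for the within-school variance of change.
- Variance of a school's mean change as the model sees it: (τ² + σ²)/m.
- True variance: τ² + σ²/m.
- Ratio: DEFF = 1 + (m − 1)ρ.
- True type I error = 2[1 − Φ(1.96/√DEFF)].

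Example, m = 8 and ρ = 0.05: DEFF = 1 + 7 × 0.05 = 1.35; 1.96/√1.35 = 1.687; error 9.2%.

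| ρ | m = 4 | m = 6 | m = 8 | m = 12 |
|---|---|---|---|---|
| 0 | 5.0% | 5.0% | 5.0% | 5.0% |
| 0.02 | 5.7% | 6.2% | 6.6% | 7.6% |
| 0.05 | 6.8% | 8.0% | 9.2% | 11.5% |
| 0.10 | 8.6% | 11.0% | 13.3% | 17.6% |
| 0.15 | 10.4% | 13.8% | 17.1% | 22.9% |

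Simulation of a single school-fixed moderator (6 schools of 10, 10 of 8, 12 of 12; 4,000 runs each; school ICC of level 0.10) gave 4.5–5.3%, 6.9–7.7%, 9.2–11.9%, 14.0–18.2% and 17.5–22.3% for the five values of ρ. The first range shows that school differences in level alone do no harm.

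**Fall and spring.** Assume unit variance per occasion and pre/post correlation 0.5, so error variance is 0.5 per occasion. One-post change then has within-school variance 1, and τ² = ρ/(1 − ρ). Mean of two posts minus baseline has error variance 0.5 × (1 + 1/2) = 0.75.
- School effect identical at both occasions: the model's residual variance is 0.5 + τ²/3, so the variance ratio is (0.75 + mτ²)/(0.75 + 0.5τ²).
- School effects independent by occasion: the residual variance is 0.5 + 2τ²/3, so the ratio is (0.75 + mτ²/2)/(0.75 + τ²).

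At ρ = 0.15, τ² = 0.15/0.85 = 0.1765. For m = 8 the ratios are 2.58 and 1.57, giving 22.2% and 11.8%, against 17.1% with one post. For m = 12 they are 3.42 and 1.95, giving 28.9% and 16.1%, against 22.9%. Two follow-up rows can therefore raise or lower the error, depending on whether the school effect persists.

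**Individual-level moderators.** If the moderator varies independently of school, simulated error stayed at 4.5–6.2% for every ρ. If the moderator itself clusters by school with ICC 0.3, then at ρ = 0.15 DEFF is about 1 + (m − 1) × 0.3 × 0.15. That is 1.315 (8.7%) for m = 8 and 1.495 (10.9%) for m = 12; simulations gave 8–14%.

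**School-level degrees of freedom.** With S schools and k school-fixed moderators together, S − 1 − k remain. For S = 6, 10, 12: k = 2 leaves 3, 7, 9; k = 4 leaves 1, 5, 7; k = 5 leaves 0, 4, 6.

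**Limits.** These are clustering-only figures. The plan's baseline covariate and its other covariates were not modelled.

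**The case against.** The strongest reply is that the harm is conditional and the setting is a pilot. At ρ = 0 there is no inflation, and nothing in the documents shows ρ to be above zero. Aim 3 is exploratory, the primary implementation outcomes are untouched, and the SAP speaks only of potential moderators. All of this stands and limits the weight of the point. It does not remove it: the same section calls T-TPQ, T-TAQ and ESMHCI-SV primary outcome measures and tests every interaction at 0.05.

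A second reply is that the interactions with organizational covariates already model school differences in change. They do so in part, which is why ρ above is the residual ICC. What they leave unexplained still produces the error.

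A reader might infer three stronger things that the documents do not support:
- That the overall post-training change is invalid. As a statement about the participating schools it is not. The documents do not state generalisation to other schools as an aim of this analysis; the nearest phrase concerns choosing measures for future trials.
- That every interaction test is compromised. Individual-level moderators are little affected if they vary independently of school. Whether role, licensure or years in the field do so is not stated.
- That there are only a few schools, or that all five organizational covariates are school-fixed. The school count is not given, and only two covariates are certainly fixed.

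**Conclusion.** The point holds in conditional form and should be fixed. That the plan specifies no allowance for school differences in change is certain. The size of the consequence is not known. If residual change varies between schools, the standard errors of the post-training by school-fixed moderator terms are too small. For 4 to 12 respondents per school and a residual ICC of 0.02 to 0.15, true type I error at a nominal 5% is about 6% to 23%. With fall and spring rows it is higher if the school effect persists across both and lower if it does not. The overall change is affected only when generalised beyond these schools. Stable school differences in level do no harm.

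**What to change.** - Test school-fixed moderators, and the overall change if it is to be generalised, on school-mean change with school-level degrees of freedom: S − 2 for one moderator, S − 1 for overall change. In simulation the moderator test held 4.6–5.8%.
- Alternatively, use CR2 school-clustered errors with Satterthwaite degrees of freedom. This was mildly conservative for moderators (2.7–4.5%), with a mean of only 2.1, 3.4 and 4.1 degrees of freedom at 6, 10 and 12 schools.
- Add a school random post-training effect, beside a school intercept, only if there are enough schools. With 6 schools the variance was estimated at zero in 17–60% of runs and moderator error fell to 0.2–3.9%. A school random intercept alone does not help, because it cancels from change.
- With few schools, test moderators one at a time and label them exploratory, or report them descriptively; with about 6 schools description may be all that is workable.
- State whether the overall change refers only to the participating schools, and whether training group structure varies within school.
- Report the number of schools, respondents per school and the between-school variance of change.

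**Cost.** SAP wording and a re-run; no new data, since school is already known. Intervals widen and power for organizational moderators is low. Even at ρ = 0, a moderator interval on S − 2 rather than participant-level degrees of freedom is wider by t ratios of 2.776/2.002 = 1.39 (6 schools of 10), 2.306/1.991 = 1.16 (10 of 8) and 2.228/1.977 = 1.13 (12 of 12).

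### A participant random intercept alone understates the standard errors for post-training change if both follow-ups are modelled and fall and spring scores correlate more with each other than with baseline

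*Combined protocol and SAP*

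**What the plan says.** The Procedure section places self-report collection before TeamSTEPPS begins and then "for the school year following participation at two time points each school year (fall, spring". That gives three occasions: baseline, fall and spring.

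Under Statistical Design and Power, Quantitative analysis, the main analysis is a linear mixed model for each of T-TPQ, T-TAQ and ESMHCI-SV, "specifying random intercepts for participant ID to account for repeated measures and within-individual clustering". Time enters as a single contrast: "The core model included a binary post-training indicator as the primary predictor", "along with the baseline value of the corresponding outcome as a covariate". The interaction models then add "full interaction terms between the post-training indicator and each individual- and organizational-level covariate", in order to "determine whether particular subgroups responded differentially to the intervention". On testing, the plan says: "Statistical significance was evaluated at the $\alpha = 0.05$ level".

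The section mentions no random slope for the post-training term, no residual correlation structure and no robust standard error. It does not say which follow-up waves enter the models. It gives no sample size, variance or between-wave correlation.

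**The concern.** A random intercept makes any two scores from one person equally correlated, whichever occasions they come from. There are two reasons to doubt this here. Fall and spring both follow training and lie in one school year. The plan also treats it as possible that people respond differently: "To examine whether training effects varied across these individual and organizational dimensions, we fitted comprehensive interaction models". If they do, a person's departure from the average change is present in fall and again in spring but absent at baseline. Fall and spring then correlate more with each other than with baseline, and the model counts the second follow-up as more new information than it carries.

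The core model is the more exposed of the two. It has no post-by-covariate terms, so any real moderation is left in it as unmodelled variation in change. In the interaction models only the variation that the listed covariates fail to explain matters.

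At stake are the confidence intervals for overall change on all three outcomes, and the 0.05 tests of moderators in work meant to guide future trials. The problem arises within a single school, so it is separate from clustering by school, and a school random intercept would not cure it.

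**Working it through.** The plan has no figure of its own to reproduce. The only number it supplies for this point is the 0.05 level, taken here as two-sided because sidedness is not stated.

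**Inputs from the documents.** Occasions coded 0, 1, 1 (baseline, fall, spring), if both follow-ups enter. Participant random intercept only. Baseline rows must be outcome rows, because otherwise the post-training indicator would be constant and could not be estimated.

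**Assumed inputs.** Equal variances scaled to 1, complete data, average baseline-to-follow-up correlation *rb*, fall-to-spring correlation *rf*.

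**Variance per participant of (mean follow-up minus baseline).**

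- True: 1 + (1 + rf)/2 − 2rb.
- Used by the random-intercept model: its residual variance is 1 − (2rb + rf)/3, so it uses 1.5 × [1 − (2rb + rf)/3].
- True minus used = rf − rb. The sign of the error therefore depends only on which correlation is larger.
- Actual error = 2 × [1 − Φ(1.96 × SE ratio)], where SE ratio = √(used/true).

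Example with rb = 0.5, rf = 0.7: true = 1 + 0.85 − 1.0 = 0.85; used = 1.5 × (1 − 1.7/3) = 0.65; SE ratio = √(0.65/0.85) = 0.874; actual error 8.7%.

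| rb | rf | True | Used | SE ratio | Actual error |
|---|---|---|---|---|---|
| 0.5 | 0.5 | 0.75 | 0.75 | 1.00 | 5.0% |
| 0.5 | 0.6 | 0.80 | 0.70 | 0.935 | 6.7% |
| 0.6 | 0.7 | 0.65 | 0.55 | 0.920 | 7.1% |
| 0.5 | 0.7 | 0.85 | 0.65 | 0.874 | 8.7% |
| 0.4 | 0.7 | 1.05 | 0.75 | 0.845 | 9.8% |
| 0.5 | 0.8 | 0.90 | 0.60 | 0.816 | 11.0% |
| 0.6 | 0.5 | 0.55 | 0.65 | 1.087 | 3.3% |

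The last row is the reversed order, where the standard error is too large. A correlation that decays with time (first-order autoregressive, 0.6 per step, equal gaps) gives a ratio of 0.926 and 7.0%.

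**The same result in terms of differing response.** Let σ² be the residual variance and τ² the between-person variance of the change. True variance is 1.5σ² + τ². The model's residual variance is σ² + τ²/3, so it uses 1.5σ² + 0.5τ². For τ²/σ² of 0, 0.5, 1, 2 and 4 the actual error is 5.0%, 6.7%, 8.0%, 9.8% and 11.8%. As τ²/σ² grows the SE ratio tends to √0.5 = 0.707, so the shortfall cannot exceed 29.3%.

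**Simulation, with the planned baseline covariate** (100 participants, 6,000 runs per setting, intercept variance equal to σ²):

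| τ²/σ² | Error, post term | Error, post × time-constant covariate |
|---|---|---|
| 0 | 5.3% | 4.8% |
| 1 | 7.6% | 8.2% |
| 2 | 9.8% | 9.1% |

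The baseline covariate does not remove the problem, and the interaction with a time-constant person covariate is affected by about the same factor.

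**Direct mixed-model fits** (60 participants, 300 runs, baseline covariate included): model SE 0.103 against a true 0.117, rejecting 9.3%. This agrees with the closed form at 0.5/0.7: √(0.65/60) = 0.104 against √(0.85/60) = 0.119. In the same check participant-clustered robust standard errors averaged 0.119 and rejected 4.3%, and change scores rejected 4.7%.

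**The case against.** The strongest objection is that every step after the algebra is conditional. Most of it stands.

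- **Waves.** The Procedure section describes data collection. The analysis section speaks of pre-to-post change and one binary indicator, and never says that both follow-ups are modelled. With one follow-up per person the random-intercept model matches the paired analysis and there is no error. This limits the point. It also exposes a plain gap, since the waves analysed should be stated in any case.
- **Direction.** A reader might infer that the standard errors are certainly too small. The documents do not support that. They give no correlations and no baseline-to-fall interval, and testing for moderators does not show that unexplained differences in response exist.
- **Which moderators.** A reader might also infer that every person-level moderator test is affected by this factor. That is shown only for covariates constant over time. Of the 11 individual-level covariates, four (three MBI subscales and the EBPAS) could vary by wave, and the plan does not say how they enter. If they vary, the factor differs.
- **Complete data is the high case.** At 0.5/0.7, if half the participants have only one follow-up (an assumption), the error falls to 7.2%; at three quarters, to 6.3%.
- **Weight.** The Procedure section makes feasibility and acceptability the primary implementation outcomes and treats teamwork and collaboration as exploratory. The analysis section nevertheless calls the three scales primary outcome measures, so this lowers the stakes without removing them.

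The objection does not reach the mechanism. The stated model cannot represent differing responses to training beyond its fixed terms, although the plan treats such differences as possible.

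**Conclusion.** The point holds conditionally and should be acted on. If both follow-ups enter, and fall and spring correlate more with each other than with baseline, the planned standard errors are too small for the post-training term and for its interactions with time-constant person-level covariates. For the five assumed pairs in which rf exceeds rb by 0.1 to 0.3, the shortfall is about 6% to 18% and the actual error 6.7% to 11.0%, with equal variances and complete data. If the two correlations are equal, or only one follow-up is used, nothing is wrong on this count; if the order is reversed, the tests are conservative. The documents do not establish which case applies, so they do not show that the intervals are in fact too narrow.

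**What to change.** 1. State which follow-up waves enter the paired tests, the main models and the interaction models.
2. If both enter, base inference for the post-training term and its interactions on participant-clustered robust standard errors with a small-sample correction. Alternatively, analyse each person's mean follow-up minus baseline, regressed on the covariates for the moderator questions, and state how a person with only one follow-up is handled.
3. A further alternative is to remove the baseline covariate, keep baseline as an outcome row, and fit an unstructured covariance over the three occasions with Kenward-Roger or Satterthwaite degrees of freedom.
4. State whether the MBI and EBPAS covariates are baseline values or vary by wave.

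In option 3 the baseline covariate has to go. With baseline on both sides of the model, a coefficient of 1 fits every baseline row exactly, and an unstructured matrix lets that row's variance fall to zero. In trial fits (60 participants, 0.5/0.7) all 15 runs failed. With the covariate removed, the model gave an SE of 0.120 against 0.121 from change scores. A random post-training slope fitted with the covariate retained did run, but its SE was about 7% too large (0.127 against 0.119).

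The cost is a short SAP revision and a refit, with no new data. Intervals widen somewhat: at 0.5/0.7 by √(0.85/0.65) = 1.14, or about 14%. If the correlations prove equal, the results should barely change.

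### The main mixed model uses each baseline score both as an outcome row and as a covariate; this adds nothing with complete data and can shrink the standard error and bias the post-training effect when follow-up is missing

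*Combined protocol and SAP*

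**What the plan says.** The Procedure section of the combined protocol and SAP sets the measurement schedule: "We will collect self-report data at baseline (i.e., before engagement in TeamSTEPPS" and then "for the school year following participation at two time points each school year (fall, spring". I read this as one wave before training and two after it. No comparison group is described.

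Under Statistical design and power, the quantitative analysis has three phases. First, "preliminary analyses were conducted using paired t-tests to evaluate simple pre-to-post changes in the primary outcome measures", namely T-TPQ, T-TAQ and ESMHCI-SV. Second, as its main analysis the plan states: "we fitted linear mixed-effects regression models for each outcome variable". Dependence within a person is handled by "specifying random intercepts for participant ID to account for repeated measures and within-individual clustering". Its fixed part is described thus: "The core model included a binary post-training indicator as the primary predictor, along with the baseline value of the corresponding outcome as a covariate". Third, interaction models add "full interaction terms between the post-training indicator and each individual- and organizational-level covariate". Testing is at 0.05.

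The text does not say which waves are outcome rows, how the indicator is coded by wave, whether participants with only a baseline score are included, or how missing follow-up is handled. It gives no sample size, expected loss or within-person correlation.

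**The concern.** In a single-group design with one pre-training wave, the post-training indicator is 0 only on baseline rows. Without those rows it is always 1 and cannot be separated from the intercept. Baseline scores must therefore be outcome rows. As the same score is also a covariate, the model contains rows in which a variable predicts itself. The true slope on the covariate is 1 on those rows and equals the pre-post correlation on follow-up rows, but the model allows only one slope.

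At stake are the post-training effect and its standard error in the main analysis of the three scales, and the moderator terms built on the same indicator. The Procedure section says the exploratory measures should help to "identify measures that are sensitive to change for future trials", and distorted effects or standard errors would make that harder.

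**Working it through.** **Inputs.** From the documents: one baseline wave, two follow-ups, participant random intercept, post indicator, baseline covariate, alpha 0.05. The plan has no figure of its own to reproduce. Assumed: outcome SD 1, true change 0, equal correlation ρ of 0.3-0.7 between waves, two-sided tests, n=80 unless stated. When a participant is lost, all follow-up is lost and the baseline row stays in. Sizes below come from REML simulation or the algebra shown.

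**1. Complete data, two follow-ups.** The covariate is constant within a participant, so the post estimate is mean follow-up minus mean baseline, with or without it. The within-participant variance is 1-ρ. Given baseline, the variance of a participant's three-wave mean is (2/9)(1-ρ)(1+2ρ). The implied random-intercept variance is therefore (2/9)(1-ρ)(1+2ρ) - (1-ρ)/3 = (1-ρ)(4ρ-1)/9. This is positive when ρ exceeds 0.25, so over the assumed range the standard error is about right (simulated model/empirical ratio 0.97-1.02).

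**2. Complete data, one follow-up only.** The common slope is (1+ρ)/2. The residuals of the two rows then have covariance -(1-ρ)²/4, which is negative, so the random-intercept variance is set to zero. The pooled residual variance is (1-ρ)(3+ρ)/4, giving a model variance of (1-ρ)(3+ρ)/(2n) against a true 2(1-ρ)/n. The SE ratio is sqrt((3+ρ)/4) = 0.91, 0.935 and 0.96 at ρ = 0.3, 0.5 and 0.7: 4-9% too small with nobody missing.

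**3. Random loss, two follow-ups.** Baseline-only rows are well predicted by their own covariate and pull the pooled variance down.
- 10% lost: SE about 2-4% too small, false positives about 5-6%.
- 30% lost: SE about 9-16% too small across simulations, false positives about 7-9%. With the covariate deleted, the SE ratio is 0.96-1.02.

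**4. Loss that depends on baseline.** Let d be the completers' baseline mean minus the overall baseline mean. The complete-pair change has bias (ρ-1)d. The model as written has bias (ρ-g)d, where g is the fitted common slope. Large-sample results at 30% loss, low scorers leaving, logit slope 1 per SD:

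| ρ | Complete-pair bias (SD) | Bias as written (SD) | Share | Implied d | Implied g |
|---|---|---|---|---|---|
| 0.3 | -0.176 | -0.085 | 0.085/0.176 = 48% | 0.176/0.7 = 0.25 | 0.64 |
| 0.5 | -0.126 | -0.066 | 0.066/0.126 = 52% | 0.126/0.5 = 0.25 | 0.76 |
| 0.7 | -0.075 | -0.042 | 0.042/0.075 = 56% | 0.075/0.3 = 0.25 | 0.87 |

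The fitted slope lies between ρ and 1, as expected. With the covariate deleted the bias is 0.000 in all three rows. A separate simulation at n=100, with one or two follow-ups, gave shares of 52-66%, so half to two-thirds is a fair summary.

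At n=80 the bias as written is about -0.05 to -0.09 SD with 11-15% false positives, nearly all of them false deterioration (11.0-14.1%). If high scorers leave, the bias is +0.04 to +0.09 SD and false improvement is 10.1-13.2%. At 10% loss with low scorers leaving, it is -0.01 to -0.03 SD with 5.7-7.4% false positives.

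**5. Interaction terms.** With 30% loss in both professional roles but baseline-dependent in only one, the post-by-role term has bias -0.04 to -0.09 SD and 8.4-9.5% false positives. With the covariate deleted: within 0.006 SD and 4.7-5.0%.

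**6. A separate matter: the random intercept.** If the follow-ups correlate r12 with each other and r01 with baseline, then with complete data the SE ratio is sqrt(1.5(1-c)/(1.5 + r12/2 - 2·r01)), where c = (2·r01 + r12)/3. For r01/r12 of 0.3/0.7: c = 0.433, and the ratio is sqrt(0.85/1.25) = 0.82. For 0.5/0.8: c = 0.6, and sqrt(0.60/0.90) = 0.82. This holds with or without the covariate.

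**The case against.** The strongest reply is that the harm rests on facts the documents do not give. With the two follow-ups in the Procedure section and complete data it is nil over the assumed correlations, and at 10% loss it is small. If only completers were analysed with two follow-ups, the SE is right under random loss. Any baseline-dependent bias (-0.08 to -0.18 SD for all enrolled at 30% loss) then comes from the exclusion, not from the covariate. All of this stands. The paired t-tests also give a partial check whose SE is valid under random loss.

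The second reply concerns the remedy. Deleting the covariate and keeping baseline-only participants works when loss is random or depends on observed scores. In a simulation with 30% loss driven by the participant's mean follow-up score (low scorers leaving, ρ = 0.5), bias was +0.10 SD as written, +0.135 SD with the covariate deleted, and +0.07 SD in completers. The order reverses. This stands and is met in the fix.

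Three stronger readings are tempting. A reader might infer that the effects already estimated are wrong; without the analysis set and the loss, that cannot be known. A reader might infer that the trial's primary result is at risk, because the analysis section calls the three scales primary outcome measures. But the Procedure section gives that place to feasibility and acceptability, which are assessed by proportions and by AIM and FIM distributions. A reader might also infer that the choice of measures for later trials turns on this test; no selection rule is stated.

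The role example needs a limit: ESMHCI-SV is documented as completed by school personnel only, so post-by-role bias applies to T-TPQ and T-TAQ.

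**Conclusion.** The double use of baseline is an inference, but the design and the indicator leave no other workable reading. The covariate cannot improve the post-training estimate with complete data. It understates the SE when baseline-only participants are kept or when only one follow-up is used, and it gives back part of the mixed model's protection when loss depends on baseline.

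The sizes illustrate the assumptions in the working; they are not estimates for this study. False positives at 30% baseline-dependent loss also grow with sample size (10-12% at n=40, 16-22% at n=160). The simulations omit the plan's other covariates and any school clustering. Confidence is high for the mechanism only. The understatement in step 6 belongs to the random-intercept structure and should not be charged to the covariate.

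As the affected analyses are exploratory outcomes of a pilot, this is a low SHOULD-FIX.

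**What to change.** In the core and interaction models, keep baseline as an outcome row, delete the baseline-value covariate, and keep participants who have baseline only. State that this relies on follow-up being missing at random given the observed scores. Report the completers-only estimate, which the paired comparison already supplies, as a sensitivity analysis, because the recommended fit can be more biased than the written one if loss depends on the unseen follow-up score.

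State which waves are outcome rows, how the indicator is coded, the analysis set, and the number of participants with each wave.

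Separately, to deal with step 6, model wave as a factor with an unstructured within-participant covariance and report the mean of fall and spring minus baseline. If that does not converge, use a random intercept with cluster-robust SEs and say that some bias may remain.

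As the models are described as already fitted, report the model as written alongside and label the change post hoc.

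The cost is a few sentences of SAP text and a re-run of three outcome models and their interaction versions on existing data. The unstructured fit has six covariance parameters instead of two, with some risk of non-convergence in a small sample.
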